If subject was not previously in XOLARIS study, BCVA assessments at baseline must be performed in triplicate.

For all subjects who require triplicate BCVA testing, to facilitate the additional BCVA measures, this visit should be conducted over 2 days, with BCVA measured twice on Day 1 and once on Day 2 (prior to pupil dilation). All 3 BCVA values must be recorded in the eCRF. The highest score will be used to define subject eligibility.

- 3. Assessments at screening collected in triplicate. To facilitate triplicate testing, the visit should be conducted over 2 days. Visual field and microperimetry outputs will be sent to a CRC for review. Data will be generated and collated within the CRC and exported to the Sponsor or designee. For microperimetry, the last assessment performed during screening will be used for assessing eligibility and will be defined as the baseline assessment.
- 4. Octopus 900 perimeter is specified for visual field assessments only in Part II.

Subjects who meet all the inclusion criteria and none of the exclusion criteria will have a study eye assigned and be enrolled into the study. In Part II, subjects will be informed of the randomisation outcome (i.e., AAV8-RPGR treatment or the Control group) and instructed to not reveal their treatment group assignment to the masked assessors during the study. Subjects randomised to the AAV8-RPGR treatment groups (along with the Investigators and sponsor) will remain masked to the assigned dose.

See Section 8.5 for details on randomisation and assignment of subject numbers.

The next study visit (Visit 2) is to be scheduled within 12 weeks of the Screening/Baseline Visit. Subjects will be given a course of oral prednisone/prednisolone and instructed to start taking the drug 2 days (Part I) or 3 days (Part II) before their next study visit (Visit 2). Where applicable, subjects will also be instructed to use barrier contraception or abstain from sexual intercourse for a period of 3 months from the time they are treated.

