1. PRIMARY REASON ONE

Section 13.1, Sample Size

In Part II, a sample size of 45 subjects, 15 in each of 3 groups (high-dose, low-dose and untreated), ensures 80% power at 0.05 significance level assuming that the treated arm has 50% probability of achieving \geq 7 dB improvement at \geq 5 loci at Month 3 vs. 5% in the untreated control arm. In Part II, the primary endpoint is the proportion of study eyes with \geq 7 dB improvement from baseline at \geq 5 of the 16 central loci of the 10-2 grid assessed by MAIA microperimetry at 12 months. A sample size of 10 subjects from a treatment group (either high dose or low dose), and 9 subjects from the untreated control group, will provide approximately 87% power, assuming the treatment group has a 50% response rate and the untreated group has a 5% response rate. The power calculation is based on Fisher Exact-Boschloo test with a Berger-Boos correction of beta = 0.001, at a right-sided significance level of 0.10.

Rationale for reduction in sample size:

Study drug expired end of September 2019, and it was not possible to extend the shelf-life, nor was there the possibility of using a new drug supply without causing a significant delay to the completion of this study.

The team performed an assessment and determined to close enrollment as of the last subject enrolled on 30 September 2019. It was decided that 29 subjects will provide sufficient data to inform the next pivotal study.

This change also affects text in Section 7.1 (Overall Study Design), 7.1.4 (Part II, Dose Expansion), and 7.2 (Number of Subjects). This sample size change also triggered broad changes to the planned statistical analyses, affecting Section 13.2 (Procedures for Accounting for Missing Data), Section 13.3.1 (Safety Analysis Set), Section 13.3.2 (Intent to Treat Analysis Set), Section 13.4 (Descriptive Statistics), Section 13.5 (Demographics and Baseline Characteristics), and Section 13.6 (Efficacy Analysis).

Section 7.1, Overall Study Design

Now reads:

Part II will expand 2 doses, allowing for a broader assessment of the safety and efficacy of AAV8-RPGR with a larger sample size, including 45 approximately 30 subjects randomized 1:1:1 to a high-dose, a low-dose, or an untreated arm.

Section 7.1.4, Part II, Dose expansion

Now reads:

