- mITT Analysis Set has been removed

The missing data imputation approaches have been updated for the primary endpoint and selected efficacy endpointsSAP Version 3.0 was amended to Version 4.0, dated on 10March 2021. The changes are summarized below:

• A protocol deviation was identified at one site which involved the use of unmasked assessors (instead of the protocol-prescribed masked assessors) conducting microperimetry, best-corrected visual acuity, low luminance visual acuity, contrast sensitivity

at the scheduled visits from Month 3 to Month 12. Sensitivity analyses are added to evaluate the impact of this deviation on these data

- Strategies for examining and excluding extreme outliers for mean sensitivity are added
- •
- Fisher's Exact Boschloo test are implemented for LLVA and BCVA change from baseline, only when the improvement is ≥10, ≥15 letters from baseline in Part II at Month 12

APPROVAL

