Three to 6 subjects are planned per dose cohort; however, the actual number of subjects enrolled into each cohort will depend on the toxicity observed. If no DLTs are observed in the first 3 subjects treated within a cohort, then escalation to the next dose cohort can proceed. If 1 DLT is reported within a 3-subject cohort, an additional 3 subjects will be added and treated at the same dose level. If there are no further DLTs reported in the additional 3 subjects, then escalation to the next dose cohort can proceed. If ≥ 2 subjects within a cohort (3 or 6 subjects) have a DLT(s), then the MTD will be identified as the previous (lower) dose. Dosing will cease under this protocol and further investigation may occur following a protocol amendment.

Part II

Approximately 30 additional subjects will be randomized in a 1:1:1 allocation ratio to a highdose group $(2.5 \times 10^{11} \text{ vg})$, a low-dose group $(5 \times 10^{10} \text{ vg})$, and an untreated control group.

Study data will be collected for both eyes of each subject. Since treatment requires an invasive surgical procedure under general anaesthesia, the sponsor, investigator and subject will be unmasked to the study procedure (i.e., vitrectomy and sub-retinal injection). However within the treated groups, the sponsor, investigator and subject will be masked to the assigned dose. To further minimise potential bias of the treated and non-treated eye evaluations, all subjective ophthalmic assessments at the Screening/Baseline Visit (Visit 1) and from Month 3 (Visit 6) onwards will be conducted by an assessor who is masked to which eye has received treatment and to which group the subject has been assigned to.

As a note, Version 6 (dated 18MAY18) of the protocol introduced the dose expansion phase of the study, where subjects were to be randomized in 2 groups (i.e., high dose and low dose) in a 2:1 allocation ratio. As of 07 November 2018, 3 subjects were randomized under the 2:1 allocation ratio as per Version 6 (prior to Version 8 finalization).

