7.6 Handling of Missing Data and Extreme Outliers

The number, pattern and timing of missing data will be examined along with the reasons for withdrawal or for missing data.

All reasonable efforts will be made to obtain complete data for both eyes on all subjects. However misisng observations may occur. In addition, due to the impact of coronavirus disease 2019 (COVID-19) on the ongoing trial, some assessments might be missed or delayed.

In Part I, although the visit will still be considered out-of-window, if subjects are unable to attend the 24-month visit during the protocol-defined window, they should return to the site to complete this visit as soon as it is possible for them to do so. This will be considered their 24-month visit. For efficacy endpoints, observations collected within 6 months of the last visit window will be included in analysis. Safety endpoints will be analyzed on observed data and no imputation will be performed. All analysis in Part I will be generated by descriptive statistics.

In Part II, although the visit will still be considered out-of-window, if subjects are unable to attend the 12-month visit during the protocol-defined window, they should return to the site to complete this visit as soon as it is possible for them to do so. This will be considered their 12-month visit. For efficacy endpoints, observations collected within 6 months of the last visit window will be included in analysis. Additional imputation approaches for the primary endpoint and selected secondary endpoints will be also implemented.

Safety analyses will be descriptive only and will be performed using the 'observed case' (OC) method. No missing data imputation will be applied to safety analyses.

The 3*IQR rule method will be used to identify the extreme outliers for the mean sensitivity. A data point is an extreme outlier if it is more than 3*IQR above the third quartile (Q3) or below the first quartile (Q1) where IQR, the interquartile range, is calculated as the absolute difference between Q3 and Q1. The influence of the extreme outliers will be investigated. The extreme outliers may be excluded from the analysis based on statistical and clinical evaluation. See section 7.12.2 on handling patients with data identified with extreme outliers in mean sensitivity analysis.

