7.12.2 MAIA Microperimetry

General considerations for Part I and Part II

When there are more than one microperimetry exam at the same visit, the latest assessment will be used for the purpose of the analysis.

MAIA microperimetry assessment is measured in decibel (dB) using a 10-2 grid of 68 points. Each point is labeled as '< 0', '0' or a positive integer (Ref. MAIA, Microperimetry Handbook). The point labeled as '< 0' is assigned a value of '-1' by MAIA in the calculation.

Improvement in Retinal Sensitivity in center grid is defined as an increase from baseline of 7 or more decibels in any 5 or more points out of the 16 central points.

Improvement in Retinal Sensitivity in whole grid is defined as an increase from baseline of 7 or more decibels in any 5 or more points of the grid as a whole (68 points).

The proportion of eyes with improved retinal sensitivity, for both the center grid and the whole grid, will be summarized by treatment groups and visit. They will be presented by study eye and fellow eye separately. The corresponding CI may be presented by using the Clopper-Pearson method.

Mean Sensitivity in center grid is defined as the mean in dB of the 16 points located in the center of the grid.

Mean Sensitivity in whole grid is defined as the mean in dB over the whole grid (all 68 points).

Mean Sensitivity, in both the center grid and the whole grid, including change from baseline will be summarized by treatment groups, visits and eyes. The corresponding CIs for actual values at each visit are calculated by one sample t-test, and for the change from baseline are calculated by paired t-test. The 3*IQR rule method is used to identify extreme outliers for the mean sensitivity change from baseline. If a subject whose mean sensitivity change from baseline from study eye or non-study eye at every post-baseline visit is > Q3+3*IQR or < Q1-3*IQR, where Q1 is the 1st quartile, Q3 is the 3rd quartile and IQR is the interquartile range, for mean change from baseline among all post-baseline visits, this subject is regarded to have anomalous mean sensitivity data and will be excluded from analysis along with clinical judgement.

For bivariate contour ellipse area 63%, bivariate contour ellipse area 95%, P1, and P2, their observed value and change from baseline will also be summarized by treatment groups and by visits. They will be presented by study eye and fellow eye separately. The corresponding CIs will be presented by one sample t-test.

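### The 3×IQR rule in SAP 7.12.2 can drop a randomised subject from the ITT mean-sensitivity comparison because of a lasting change in either eye, and its reference pool is only partly defined

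*SAP*

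**What the plan says.** The rule is in the general considerations of SAP 7.12.2, which cover Parts I and II. A subject is flagged when the change in mean sensitivity "from study eye or non-study eye at every post-baseline visit" lies outside the 3×IQR fences; then "this subject is regarded to have anomalous mean sensitivity data and will be excluded from analysis along with clinical judgement". The quartiles are described as taken over all post-baseline visits. Nothing says whether they are taken across or within arms, across or within eyes, on the 16- or 68-point grid, or across Parts.

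SAP 7.6 is softer: "The extreme outliers may be excluded from the analysis based on statistical and clinical evaluation". It also promises to look into the influence of outliers, without naming an analysis, and sends the reader to 7.12.2 for how such patients are handled. Neither section says who exercises the clinical judgement or whether that person is masked to arm.

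SAP 7.1 and 7.12.1 assign Part II efficacy to the ITT set. For change in mean sensitivity, 7.12.2 calls for observed data to be used whatever intercurrent events occur, a two-sample t-test with CI and p-value at each visit, and multiple imputation by locus followed by an MMRM with a nominal pooled p-value. Under 7.12.1, fellow eyes are only described.

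SAP Section 2 records that Version 3.0 was "amended to Version 4.0, dated on 10March 2021", and lists among the changes: "Strategies for examining and excluding extreme outliers for mean sensitivity are added".

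**The concern.** Membership of the analysis depends on the result being analysed. A sustained fall in sensitivity after subretinal surgery is a harm signal, and a sustained rise is the intended benefit; either can meet the trigger. An extreme untreated fellow eye also takes the randomised study eye out of the between-arm comparison.

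The text does not define a unique calculation. Two analysts with different pools can keep or drop the same subject and both be following the plan. With 9 or 10 eyes per arm, one subject matters.

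The SAP handles similar problems differently elsewhere. Microperimetry from the site with unmasked assessors stays in the main analysis, and leaving it out is a sensitivity analysis (7.12.2). Visual fields (7.12.7) are screened by a reliability factor that does not depend on the result, with tables of all records and a listing that marks the reliable ones. Mean sensitivity has neither safeguard.

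**Working it through.** **The plan's own figures.** The SAP gives no SD for mean sensitivity and no operating characteristic for the rule. Its only power figure is about 87% for the primary responder endpoint (SAP 6.6: 10 v 9, 50% v 5%, one-sided 0.10, Boschloo with Berger-Boos 0.001). Exact enumeration gives 86.8%. The rule is not written for that endpoint, so the figure stands.

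**Inputs from the documents.** Arms of 10, 10 and 9 (SAP 6.6); six post-baseline visits, at months 1, 2, 3, 6, 9 and 12 (SAP 5.2.2.3); study-eye mean total sensitivity at entry 0.1 to 8 dB (Protocol 7.2.1); scale floor −1 dB (SAP 7.12.2).

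**Assumptions.** A locus-change SD of 4 dB with independent loci gives an SD of the mean change of 4/√68 = 0.49 dB on the whole grid and 4/√16 = 1.0 dB on the central 16. Half of the error variance is shared across visits (baseline error). Half of treated eyes truly gain 5×7/16 = 2.19 dB; untreated and fellow eyes change by 0.

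**Step 1: ordinary noise.** For normal noise about 0 the fence is 0.674 + 3×1.349 = 4.72 SD, i.e. ±2.36, ±3.54 and ±4.72 dB at SD 0.5, 0.75 and 1.0, and it must be passed at all six visits. With no extreme eye, fewer than 0.02 subjects per simulated trial are dropped.

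**Step 2: leverage of one eye.** Let the other nine eyes average +1.10 dB (half of 2.19).
- One eye at −6: (9×1.10 − 6)/10 = 0.39 with it, 1.10 without it; shift +0.71 dB.
- One eye at −4: (9×1.10 − 4)/10 = 0.59; shift +0.51 dB.
- One eye at +7: (9×1.10 + 7)/10 = 1.69; shift −0.59 dB.

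**Step 3: how often one high-dose eye at −6 dB is dropped.** Ranges show the spread between repeat runs.

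| SD of mean change | Between-subject SD of true change | Pool: both eyes, all arms | Pool: study eyes, all arms | Pool: by arm and eye |
|---|---|---|---|---|
| 0.5 | none | 99.7% | 32% | 24% |
| 0.75 | none | 88% | 25% | 21% |
| 1.0 | none | 31% | 10% | 13% |
| 0.5 | 1 dB | 28% | 13–15% | 19–21% |
| 1.0 | 1 dB | 2% | 2% | 6–9% |

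In the first row, the mean high-minus-untreated difference is +0.38 dB with all subjects and +1.08, +0.60 or +0.55 dB after the rule, in the same pool order.

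**Step 4: a second variance model** (one eye per subject; fences from all arms pooled, or within arm). One high-dose eye at −8 dB is dropped in 100% or 99.7% of runs at between-/within-subject SD 0.75/0.5, 87% or 80% at 1/0.75, 11% or 20% at 1.5/1, and 1% or 8% at 2/1. In the other direction, if 20% of treated eyes gain about 8 dB (SD 0.75/0.5), at least one subject is dropped in 90% or 74% of runs, and the difference of 1.59 dB falls by 1.16 or 0.56 dB.

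**The case against.** The strongest reply concerns size. The near-certain exclusion in the first table row needs a narrow IQR: whole-grid SD, no between-subject variation, and fellow eyes pooled with study eyes. A between-subject SD of 1 dB cuts 99.7% to 28%, and at the central-grid SD of 1.0 to 2%. The loss is also near the limit of the scale: with a floor of −1 dB, a 6 dB whole-grid fall needs a baseline of at least 5 dB when entry allows at most 8. All of this stands, so no single probability should be presented as the expected one.

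Second, exclusion is tempered by clinical judgement, and SAP 7.6 promises to investigate influence. That stands in part. The judgement is unassigned and not said to be masked, and no analysis with and without the flagged subjects is specified.

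Third, the rule sits in a paragraph on summaries, and the t-test and MMRM text does not repeat it. Its reach is therefore ambiguous, although excluding a subject from analysis most naturally covers both.

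Fourth, a reader might infer that exclusion is tied to the treated arms and hides harm. The SAP's rationale for LOCF expects durable benefit in treated eyes and slow change in untreated ones. That supports an arm link for gains, whose removal would count against the product, but not for losses. Common responders also widen the IQR: with half of treated eyes gaining 8 dB, a subject is dropped in only 9% (pooled) or 19% (within arm) of runs in the second model at SD 0.75/0.5.

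**Conclusion.** The point holds as a fault in a secondary analysis that should be corrected. The rule conditions an ITT comparison on the outcome, lets a fellow eye remove a study eye, and cannot be computed uniquely from the text. For one high-dose eye at −6 dB, the chance of exclusion runs from about 2% to nearly 100% across assumed SDs and pools. If it happens, the arm mean shifts by about 0.7 dB, and a dropped gain shifts it the other way. The SDs and effects are assumptions; the documents supply none. The primary endpoint, its alpha and its power are unaffected.

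A reader might also infer that the rule was written after results by arm had been seen. The Version 11 amendment summary records the decision to "close enrollment as of the last subject enrolled on 30 September 2019", and Protocol 9.1 says "The next study visit (Visit 2) is to be scheduled within 12 weeks of the Screening/Baseline Visit". Taking the full interval, 30 September 2019 + 84 days = 23 December 2019; adding 12 months and 14 days gives 6 January 2021, which is 63 days before 10 March 2021. SAP 6.1 adds that "the sponsor, investigator and subject will be unmasked to the study procedure". But the date assumes the longest permitted gap for the last subject, and SAP 7.3 accepts Month 12 visits up to 6 months out of window, so collection may still have been open. Nothing in the documents shows that anyone had examined data by arm. The timing is a reason for transparency and is not evidence of a data-driven choice.

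**What to change.** 1. State that the main mean-sensitivity analyses (t-test and multiple imputation with MMRM) use all ITT subjects, with no exclusion based on the outcome.
2. Keep 3×IQR only as a labelled sensitivity analysis. State the pool, for example study eyes by arm and grid, and flag the eye, so that a fellow-eye flag does not remove the study eye.
3. Reject a record from the main analysis only on grounds independent of the result: a technical fault, or a baseline that disagrees with the other Visit 1 examinations (Protocol 10.4 requires three). Assign that decision to staff masked to arm.
4. List every flagged eye by arm with its value at each visit, and give SAP 7.6 and 7.12.2 the same wording. If the rule has already been applied, report both versions, with the all-ITT result first.

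The cost is SAP wording, one analysis run without the exclusion, and one listing; no new data are needed. The downside is that a faulty record stays in the main analysis unless it can be rejected on technical grounds.

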12.6. Efficacy Analyses

Efficacy assessments are ocular in nature and therefore will be tabulated by eye (Study Eye and Fellow Eye). In Part I, efficacy endpoints will be summarised on observed data using descriptive statistics only (described in Section 12.4). In Part II, efficacy endpoints will be summarized on observed data using descriptive statistics. Additional analyses for handling missing data will be provided for the primary endpoint and selected secondary endpoint.

For each subject, data collected within 6 months of the last visit window will be included in the primary analysis, as described in greater detail in the SAP.

At final analysis in Part II, the primary endpoint, which is defined as the proportion of study eyes with ≥7 dB improvement from baseline at ≥5 of the 16 central loci at 12 months, will be compared between treatment groups (high dose vs untreated; low dose vs untreated) using the Fisher Exact-Boschloo test with a Berger-Boos correction of beta=0.001 (Berger and Boos 1994). The CIs for the difference in proportions between treatment groups will be presented by Miettinen and Nurminen (Miettinen and Nurminen 1985) method.

For the continuous variables of mean sensitivity, BCVA, and LLVA in Part II, the primary analysis to handle missing data uses a mixed model repeated measures (MMRM) model. The mean change from baseline will be analyzed using fixed effects of treatment group, study visit, study-visit-treatment interaction, and baseline value.

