7.5 Adjustment for Multiplicity

Part I

This is the dose-escalation part of the study to identify the MTD based on the evaluation of the benefit-risk without any formal statistical comparison. Adjustment for multiplicity is, therefore not applicable.

Part II

The primary efficacy endpoint of Part II is defined as the proportion of study eyes with \geq 7 dB improvement from baseline at \geq 5 of the 16 central loci of the 10-2 grid assessed by MAIA microperimetry at 12 months.

At final analysis, the primary endpoint will be tested byHochberg's (Hochberg 1988) step-up method with familywise error rate controlled at right-sided 0.10. The high dose vs. control group, and the low dose vs. control group will be tested respectively. The study will be declared positive if either dose or both doses achieve statistical significance.

Two hypotheses will be tested for primary endpoint:

High dose vs control group:

 $H_0: p_{trt} = p_{untr} \ versus \ H_1: p_{trt} > p_{untr}$

Low dose vs control group:

H₀: $p_{trt} = p_{untr}$ versus H₁: $p_{trt} > p_{untr}$

The algorithm is based on data-driven ordering of hypotheses $H_{(1)}$ and $H_{(2)}$ corresponding to the ordered p-values $P_{(1)} < P_{(2)}$.

Step 1: start with larger p-value $P_{(2)}$. If $P_{(2)} < 0.10$ (one-sided) then reject null hypotheses and claim this test is significant. The remaining hypothesis test is also rejected. Both doses achieve statistical significance. Otherwise if $P_{(2)} \ge 0.10$ this is not significant and proceed to the next test to compare $P_{(1)}$ with 0.05 (one-sided).

Step 2: if $P_{(1)} < 0.05$ (one-sided) then testing stops. The dose associated with $P_{(1)}$ is claimed statistically significant than control group. The dose associated with $P_{(2)}$ is not statistically significant. Or if $P_{(1)} \ge 0.05$ (one-sided) then testing stops and both doses are not statistically significant.

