The proportion of eyes with improved retinal sensitivity, for both the center grid and the whole grid, at Month 12 will be compared between study arms (high dose vs untreated; low dose vs untreated) using the Fisher's Exact-Boschloo test with a Berger-Boos correction of beta=0.001 (Berger 1994). The difference in proportions between treatment groups will be presented with its corresponding 80% CI calculated using the method of Miettinen and Nurminen (Miettinen 1985).

• Primary Endpoint:

The intercurrent event is discontinuation of study early or lost to follow-up for this study. The estimand is the response rate difference between treatment and control group in ITT Analysis Set regardless of intercurrent events. The treatment policy strategy will be used for the intercurrent events. Observed data collected within 6 months outside the last visit window will be included in the analysis, including data collected after intercurrent events [ICH E9(R1) addendum 2019], i.e. discontinuation of study early or lost to follow-up.

For other missing data due to intercurrent events or other reasons, the following missing data imputation methods will be provided.

Primary analysis for missing data imputation:

The last observation carried forward method (LOCF) will be applied to the underlying continuous variables of retinal sensitivity. The imputed value will then be dichotomized based on the responder criteria, i.e., improvement of \geq 7 dB from baseline. Imputation of retinal sensitivity will be done at locus level, i.e. if a locus value is missing at a visit, the last non-missing value will be carried over to this visit.

This is a hypothetical strategy based on the assumption that the retinal sensitivity of subjects who are discontinued from the study early or lost to follow up will remain unchanged from the last observed value until the month-12 visit. This is considered a plausible assumption due to 1) the slow progression of the disease for the untreated eyes, and 2) the durability of efficacy demonstrated for the treated eyes for up to 18 months based on the current Part I data.

In addition to the primary analysis, 2 supplementary analyses are proposed under different assumptions for the estimand to assess efficacy in subjects who have missing data.

Supplementary analysis for missing data imputation:

Supplementary Analysis I:

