The composite strategy will be used for the intercurrent event. The non-responder imputation method will be applied on locus level. i.e. if a locus value is missing at a visit, it will be imputed as a failure. This is a conservative approach in that any missing data will be considered as a non-responder.

Supplementary Analysis II:

The hypothetical strategy will be used with the assumption that the retinal sensitivity of the subjects who have discontinued the study early or lost to follow-up will be similar to those subjects who remain in the study. The multiple imputation approach will be applied to the missing data on the locus level under the assumption of missing-at-random (MAR). MAR assumption is considered plausible since treatment is only administered once for gene therapy after randomization in the study. Subjects do not take ongoing doses after surgery. Subjects who are lost to follow up or drop out early are not related to the effect of ongoing dose taken. These missing data are regarded missing at random. The missing retinal sensitivity data at each locus will be imputed by the method of multiple imputation. Each imputed data set will be analyzed using two-sample Binomial test. The analyzed results from the imputed dataset will be combined based on Rubin's rule (Rubin 1987) for inference assuming the statistics estimated from each imputed dataset are normally distributed.

Sensitivity analysis

It was identified that microperimetry data from one site were impacted by a protocol deviation involving assessments conducted by an unmasked rather than masked assessor from month 3 to month 12. Microperimetry is an automated test that measures the minimum luminance of a light stimulus that can be perceived by a subject at defined locus of the retina. The impact of an unmasked assessor on results is limited due to the automated nature of the test, in that the assessor is not directly involved in generating or recording the results. In addition, the perceived light stimulus at a specific locus is tested by projecting multiple stimulus points of varying light intensities. The projection strategies further reduce the probability of an unmasked assessor significantly impact the data. However, an unmasked assessor can still introduce bias into the results in indirect ways, e.g., by encouraging the subject to stay focused during the test. The risk of significantly altering microperimetry results by an unmasked assessor is believed low.

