7.16 Selected Algorithms/SAS Codes

• Descriptive statistics for continuous variables:

PROC UNIVARIATE DATA=dset NOPRINT; VAR var1 var2 var3 ...varn; BY byvar; (optional) OUTPUT OUT=outname N=n MEAN=mean MIN=min MAX=max MEDIAN=median STD=std P5=p5 P95=p95 Q1=q1 Q3=q3; RUN;

• 80% CIs for mean of observed (actual) value- one sample t-test:

proc ttest data=sample alpha=0.20; class treatment; var endpoint; run;

• 80% CIs for mean change from baseline- paired ttest formula:

```
proc ttest data=dset alpha = 0.20;
paired var1*var2;
run;
```

• Clopper-Pearson 80% CIs within group for binomial proportions:

proc freq data=one; tables response/binomial (exact) alpha=0.20 missprint; weight count; run;

• 80% CI for difference in proportion by the method of Miettinen and Nurminen

```
Proc freq data=dataset noprint;
tables group*outname/riskdiff(cl=mn) measure alpha = 0.20;
Output out = outname;
Run;
```

• Mixed Model Repeated Measures (MMRM)

Proc mixed DATA = data; CLASS subjid tr01pg1 visit; MODEL chg = tr01pg1 bs visit visit*tr01pg1 bs*visit / DDFM=KENWARDROGER Solution; REPEATED visit / TYPE=UN SUBJECT=subjid; LSMEANS visit*tr01pg1/cl pdiff; Run;

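### Does an unadjusted 80% CI beside a Hochberg decision, or the Rubin-pooled binomial test, call for a change to the SAP?

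*SAP*

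**What the plan says.** SAP 7.5 tests each dose against control by Hochberg with "familywise error rate controlled at right-sided 0.10". If the larger p-value is below 0.10, both doses are significant. If not, "this is not significant and proceed to the next test to compare" the smaller p-value with 0.05. The success rule is "The study will be declared positive if either dose or both doses achieve statistical significance". The p-values come from the Boschloo test with a Berger-Boos correction of 0.001.

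Beside the test, SAP 7.12.2 specifies: "The difference in proportions between treatment groups will be presented with its corresponding 80% CI calculated using the method of Miettinen and Nurminen". The SAP 7.16 code is headed "80% CI for difference in proportion by the method of Miettinen and Nurminen" and sets alpha to 0.20 for each comparison. Protocol 12.6 names the method but no level: "The CIs for the difference in proportions between treatment groups will be presented by Miettinen and Nurminen".

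Missing data in the primary analysis are handled by LOCF at locus level. Supplementary Analysis II in SAP 7.12.2 uses multiple imputation instead: "Each imputed data set will be analyzed using two-sample Binomial test". Results are pooled by Rubin's rule "for inference assuming the statistics estimated from each imputed dataset are normally distributed".

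**The concern.** The interval and the test use different standards in two respects. The interval carries no allowance for two doses, whereas Hochberg may require 0.05. It is also an asymptotic score interval beside an exact test. No sentence in the SAP says that the interval is unadjusted. A report could therefore show a dose with an interval wholly above zero that was declared not significant, and a reader might take the interval as evidence of success.

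The second worry is that a normal-theory test with 10 and 9 subjects may reject too often, so that the supplementary p-value looks more favourable than the exact primary one. The SAP does not state the variance form for that test.

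What is at stake is how the results read. Neither output enters the Hochberg decision.

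**Working it through.** **Inputs.** 10 treated, 9 control, response rates 50% and 5% (SAP 6.6); Hochberg at one-sided 0.10, then 0.05 (SAP 7.5); 80% Miettinen-Nurminen interval (SAP 7.12.2, 7.16). All tables were enumerated exactly.

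**The SAP's own figure.** Summing the binomial probabilities of all tables with Boschloo/Berger-Boos p < 0.10 gives power 86.8%, against the stated 87%.

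**When the interval lies above zero.** The lower limit exceeds 0 when the score statistic at zero difference exceeds 1.282 (80%) or 1.645 (90%):

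z = (p1 − p2) / √[ p̄(1 − p̄)(1/10 + 1/9)(19/18) ], with p̄ = (x1 + x2)/19.

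Example, 6/10 vs 2/9: p̄ = 8/19 = 0.421; variance 0.421 × 0.579 × 0.2111 × 1.0556 = 0.0543; z = 0.378/0.233 = 1.62. The 80% interval is 0.08 to 0.61, yet the exact p is 0.060. This dose passes if the other dose also has p < 0.10 and fails otherwise.

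**All conflicting tables.** The 80% interval is above zero in 32 tables. Of these, 24 have p < 0.05. The other eight are:

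| Table | Exact p | 80% lower limit |
|---|---|---|
| 2/10 vs 0/9 | 0.179 | 0.023 |
| 3/10 vs 0/9 | 0.063 | 0.117 |
| 4/10 vs 1/9 | 0.096 | 0.024 |
| 6/10 vs 2/9 | 0.060 | 0.081 |
| 7/10 vs 3/9 | 0.075 | 0.065 |
| 8/10 vs 4/9 | 0.087 | 0.065 |
| 9/10 vs 5/9 | 0.060 | 0.083 |
| 10/10 vs 7/9 | 0.093 | 0.058 |

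Seven conflict only at the 0.05 step; 2/10 vs 0/9 fails even at 0.10. In the other direction there is no conflict: every table with p < 0.10 has an 80% interval above zero. The 80% level therefore agrees with the unadjusted 0.10 test in all but one table.

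**How often (10/10/9, shared control).**

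| True rates high/low/control | Some dose has CI above 0 but fails | CI above 0 and no dose declared |
|---|---|---|
| 50/5/5% | 21.5% | 17.6% |
| 50/50/5% | 9.4% | 4.9% |
| 5/5/5% | 10.3% | 10.3% |

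Over common rates from 5% to 95% in 5-point steps, Hochberg's familywise error peaks at 8.3%, below 10%. For a single comparison, the chance under the null that the 80% interval lies above zero peaks at 12.5%, against a nominal 10%.

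**Would another level help?** Share of trials with any mismatch between interval and decision, in either direction:

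| Rates | 80% for all | 90% for all | 80% if both doses reject, otherwise 90% |
|---|---|---|---|
| 50/50/5% | 9.4% | 10.4% | 0.8% |
| 50/5/5% | 21.5% | 7.4% | 7.3% |

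A flat 90% level creates conflicts the other way, with rejected doses whose interval covers zero. The level that depends on the Hochberg step still leaves 3/10 vs 0/9 (90% lower limit 0.025) and 9/10 vs 5/9 (0.003).

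**Supplementary Analysis II, complete data, z = (p1 − p2)/SE.**

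| Variance | Nominal one-sided | Maximum size | Size at 5% common rate |
|---|---|---|---|
| Pooled | 10% | 12.5% | 5.5% |
| Unpooled | 10% | 13.2% | 5.5% |
| Pooled | 5% | 6.2% | 0.7% |
| Unpooled | 5% | 8.6% | 0.7% |

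At nominal 10% the size exceeds nominal only for common rates of about 9% to 33% (pooled) or 9% to 53% (unpooled). The SAP gives neither a missing-data rate nor its imputation model. Assuming 10% to 20% missing and a subject-level imputation, simulated size at nominal 10% is 2.8% to 4.4% at a 5% common rate. Under a similar assumed model with 1 to 3 missing per arm, the maximum over common rates is 12.1% to 14.1%.

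**The case for a change.** The best case for a change is that the conflict is not rare. Under the SAP's own rates, with only one dose working, about one trial in five would print an interval above zero for a failed dose. The interval belongs to the primary estimand, the response rate difference, and its level could be altered without a protocol amendment. All of that is correct.

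It still does not show a defect in the plan. SAP 7.5 settles, step by step, which dose is significant, using p-values alone. The protocol synopsis introduces the interval as an additional presentation. A per-comparison interval beside a multiplicity-adjusted test is common practice.

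The alternatives are not clearly better. A step-dependent level is chosen after seeing both p-values, has no demonstrated coverage, and gains nothing over a flat 90% at 50/5/5% (7.3% against 7.4%). Inverting the exact test removes the conflict only with that same level switch. It needs real programming and changes no conclusion.

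On Supplementary Analysis II, the missing variance form is a true gap. Sidedness is less so: SAP 7.5 and 7.12.2 write the hypotheses for this endpoint one-sided. The normality assumption is stated openly, and non-responder imputation, which the SAP itself calls conservative, is reported as well. Judging instead on an upper quantile, such as the 75th percentile, of exact p-values across imputations would be ad hoc. With 1 missing per arm under the assumed model, it costs about 6 points of power (88% to 82%).

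**Conclusion.** The observation about the interval is right; it does not require a change. The 80% interval is an unadjusted, per-comparison description that can lie above zero for a dose failing Hochberg: 8 of 32 tables, seven of them only at the 0.05 step, and 21.5% of trials at 50/5/5% or 9.4% at 50/50/5%. The declaration and its familywise error (at most 8.3% over the rates checked) are unaffected. Report authors can be expected to label such intervals as unadjusted and to take significance from SAP 7.5.

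The claim that the pooled binomial test is too liberal holds only as a worst case: 2.5 to 3.2 points above nominal 10% with complete data, at common rates of about 9% or more. At the SAP's 5% control rate it is conservative. An analyst will have to choose a variance form, and either choice leaves the primary result as it is.

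These figures assume 10/10/9 subjects. The complete-data results are exact; those with missing data rest on assumed missing rates and a subject-level stand-in for the SAP's locus-level imputation.
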